10.3.3. Recording and Follow-Up of AE and/or SAE**AE and SAE Recording**

- When an AE/SAE occurs, it is the responsibility of the investigator to review all documentation (e.g., hospital progress notes, laboratory reports, and diagnostics reports) related to the event.
- The investigator will then record all relevant AE/SAE information in the CRF.
- It is **not** acceptable for the investigator to send photocopies of the participant's medical records in lieu of completion of the AE/SAE CRF page.
- There may be instances when copies of medical records for certain cases are requested by sponsor. In this case, all participant identifiers, with the exception of the participant number, will be redacted on the copies of the medical records before submission to sponsor.
- The investigator will attempt to establish a diagnosis of the event based on signs, symptoms, and/or other clinical information. Whenever possible, the diagnosis (not the individual signs/symptoms) will be documented as the AE/SAE.

Assessment of Intensity

The investigator will make an assessment of intensity for each AE and SAE reported during the study and assign it to 1 of the following categories:

- Mild: An event that is easily tolerated by the participant, causing minimal discomfort and not interfering with everyday activities.
- Moderate: An event that causes sufficient discomfort and interferes with normal everyday activities.
- Severe: An event that prevents normal everyday activities. An AE that is assessed as severe should not be confused with a SAE. Severe is a category utilized for rating the intensity of an event; and both AEs and SAEs can be assessed as severe.

An event is defined as ‘serious’ when it meets at least 1 of the predefined outcomes as described in the definition of an SAE, NOT when it is rated as severe.

Assessment of Causality

- The investigator is obligated to assess the relationship between study intervention and each occurrence of each AE/SAE.
- A “reasonable possibility” of a relationship conveys that there are facts, evidence, and/or arguments to suggest a causal relationship, rather than a relationship cannot be ruled out.
- The investigator will use clinical judgment to determine the relationship.
- Alternative causes, such as underlying disease(s), concomitant therapy, and other risk factors, as well as the temporal relationship of the event to study intervention administration will be considered and investigated.
- The investigator will also consult the Investigator’s Brochure (IB) and/or Product Information, for marketed products, in his/her assessment.
- For each AE/SAE, the investigator **must** document in the medical notes that he/she has reviewed the AE/SAE and has provided an assessment of causality.
- There may be situations in which an SAE has occurred and the investigator has minimal information to include in the initial report to the sponsor. However, it is very important that the investigator always make an assessment of causality for every event before the initial transmission of the SAE data to sponsor.
- The investigator may change his/her opinion of causality in light of follow-up information and send a SAE follow-up report with the updated causality assessment.
- The causality assessment is one of the criteria used when determining regulatory reporting requirements.

Follow-up of AEs and SAEs

- The investigator is obligated to perform or arrange for the conduct of supplemental measurements and/or evaluations as medically indicated or as requested to elucidate the nature and/or causality of the AE or SAE as fully as possible. This may include additional laboratory tests or investigations, histopathological examinations, or consultation with other health care professionals.
- If a participant dies during participation in the study or during a recognized follow-up period, the investigator will provide sponsor with a copy of any post-mortem findings including histopathology.
- New or updated information will be recorded in the originally completed CRF.
- The investigator will submit any updated SAE data to sponsor within 24 hours of receipt of the information.

10.3.4. Reporting of SAEs**SAE Reporting to Sponsor via an Electronic Data Collection Tool**

- The primary mechanism for reporting an SAE to sponsor will be the electronic data collection tool.
- If the electronic system is unavailable, then the site will use the paper SAE data collection tool (see next section) in order to report the event within 24 hours.
- The site will enter the SAE data into the electronic system as soon as it becomes available.
- After the study is completed at a given site, the electronic data collection tool will be taken off-line to prevent the entry of new data or changes to existing data.
- If a site receives a report of a new SAE from a study participant or receives updated data on a previously reported SAE after the electronic data collection tool has been taken off-line, then the site can report this information on a paper SAE form (see next section) or to the Lilly Medical by telephone.

SAE Reporting to Sponsor or designee via Paper CRF

- Facsimile transmission of the SAE paper CRF is the preferred method to transmit this information to the Lilly Medical.
- In rare circumstances and in the absence of facsimile equipment, notification by telephone is acceptable with a copy of the SAE data collection tool sent by overnight mail or courier service.
- Initial notification via telephone does not replace the need for the investigator to complete and sign the SAE CRF pages within the designated reporting time frames.

10.4. Appendix 4: Contraceptive Guidance and Collection of Pregnancy Information

Definitions:

Woman of Childbearing Potential (WOCBP)

A woman is considered fertile following menarche and until becoming post-menopausal unless permanently sterile (see below).

If fertility is unclear (e.g., amenorrhea in adolescents or athletes) and a menstrual cycle cannot be confirmed before first dose of study intervention, additional evaluation should be considered.

Women in the following categories are not considered WOCBP

1. Premenarchal
2. Premenopausal female with 1 of the following:
 - Documented hysterectomy
 - Documented bilateral salpingectomy
 - Documented bilateral oophorectomy

For individuals with permanent infertility due to an alternate medical cause other than the above, (e.g., mullerian agenesis, androgen insensitivity), investigator discretion should be applied to determining study entry.

Note: Documentation can come from the site personnel's: review of the participant's medical records, medical examination, or medical history interview.

3. Postmenopausal female is defined as, women with:
 - i. A woman at least 40 years of age with an intact uterus, not on hormone therapy, who has cessation of menses for at least 1 year without an alternative medical cause, AND a follicle-stimulating hormone >40 mIU/mL; or
 - ii. A woman 55 or older not on hormone therapy, who has had at least 12 months of spontaneous amenorrhea; or
 - iii. A woman at least 55 years of age with a diagnosis of menopause prior to starting hormone replacement therapy.

The investigator will attempt to collect pregnancy information on any male participant's female partner who becomes pregnant while the male participant is in this study. This applies only to male participants who receive study intervention.

After obtaining the necessary signed informed consent from the pregnant female partner directly, the investigator will record pregnancy information on the appropriate form and submit it to the sponsor within 24 hours of learning of the partner's pregnancy. The female partner will also be followed to determine the outcome of the pregnancy. Information on the status of the mother and child will be forwarded to the sponsor. Generally, the follow-up will be no longer than 6 to 8 weeks following the estimated delivery date. Any termination of the pregnancy will be reported regardless of fetal status (presence or absence of anomalies) or indication for the procedure.

Female Participants who become pregnant

The investigator will collect pregnancy information on any female participant who becomes pregnant while participating in this study. The initial information will be recorded on the appropriate form and submitted to the sponsor within 24 hours of learning of a participant's pregnancy.

The participant will be followed to determine the outcome of the pregnancy. The investigator will collect follow-up information on the participant and the neonate and the information will be forwarded to the sponsor. Generally, follow-up will not be required for longer than 6 to 8 weeks beyond the estimated delivery date. Any termination of pregnancy will be reported, regardless of fetal status (presence or absence of anomalies) or indication for the procedure.

While pregnancy itself is not considered to be an AE or SAE, any pregnancy complication or elective termination of a pregnancy for medical reasons will be reported as an AE or SAE.

A spontaneous abortion (occurring at <22 weeks gestational age) or still birth (occurring at >22 weeks gestational age) is always considered to be an SAE and will be reported as such.

Any post-study pregnancy related SAE considered reasonably related to the study intervention by the investigator will be reported to the sponsor as described in Section 8.3.4. While the investigator is not obligated to actively seek this information in former study participants, he or she may learn of an SAE through spontaneous reporting.

Any female participant who becomes pregnant while participating in the study will discontinue study intervention or be withdrawn from the study.

10.5. Appendix 5: Liver Safety: Suggested Actions and Follow-up Assessments

Hepatic Monitoring Tests

Hepatic Hematology^a	Haptoglobin^a
Hemoglobin	
Hematocrit	Hepatic Coagulation^a
RBC	Prothrombin Time
WBC	Prothrombin Time, INR
Neutrophils, segmented	
Lymphocytes	Hepatic Serologies^{a,b}
Monocytes	Hepatitis A antibody, total
Eosinophils	Hepatitis A antibody, IgM
Basophils	Hepatitis B surface antigen
Platelets	Hepatitis B surface antibody
	Hepatitis B Core antibody
Hepatic Chemistry^a	Hepatitis C antibody
Total bilirubin	Hepatitis E antibody, IgG
Direct bilirubin	Hepatitis E antibody, IgM
Alkaline phosphatase	
ALT	Anti-nuclear antibody^a
AST	
GGT	Alkaline Phosphatase Isoenzymes^a
CPK	
	Anti-smooth muscle antibody (or anti-actin antibody)^a

Abbreviations: ALT = alanine aminotransferase; AST = aspartate aminotransferase; CPK = creatinine phosphokinase; GGT = gamma-glutamyl transferase; Ig = immunoglobulin; INR = international normalised ratio; RBC = red blood cells; WBC = white blood cells.

a Assayed by sponsor-designated or local laboratory.

b Reflex/confirmation dependent on regulatory requirements and/or testing availability.

10.6. Appendix 6: New York Heart Association Cardiac Disease Classification

Functional Capacity

Class I

Patients with cardiac disease but without resulting limitation of physical activity. Ordinary physical activity does not cause undue fatigue, palpitation, dyspnea, or anginal pain.

Class II

Patients with cardiac disease resulting in slight limitation of physical activity. They are comfortable at rest. Ordinary physical activity results in fatigue, palpitation, dyspnea, or anginal pain.

Class III

Patients with cardiac disease resulting in marked limitation of physical activity. They are comfortable at rest. Less than ordinary activity causes fatigue, palpitation, dyspnea, or anginal pain.

Class IV

Patients with cardiac disease resulting in inability to carry on any physical activity without discomfort. Symptoms of heart failure or the anginal syndrome may be present even at rest. If any physical activity is undertaken, discomfort increases.

1994 Revisions to Classification of Functional Capacity and Objective Assessment of Patients with Diseases of the Heart

Reprinted with permission

www.americanheart.org

© 2011, American Heart Association, Inc.

10.7. Appendix 7: Genetics

Use/Analysis of DNA

Genetic variation may impact a participant's response to study intervention, susceptibility to, and severity and progression of disease. Variable response to study intervention may be due to genetic determinants that impact drug absorption, distribution, metabolism, and excretion; mechanism of action of the drug; disease etiology; and/or molecular subtype of the disease being treated. Therefore, where local regulations and IRB/IEC allow, a blood sample will be collected for DNA analysis from consenting participants.

DNA samples will be used for research related to study intervention or T1DM and related diseases. They may also be used to develop tests/assays including diagnostic tests related to study intervention and/or interventions of this drug class and T1DM. Genetic research may consist of the analysis of one or more candidate genes or the analysis of genetic markers throughout the genome or analysis of the entire genome (as appropriate).

The samples may be analyzed as part of a multi-study assessment of genetic factors involved in the response to study intervention or study interventions of this class to understand study disease or related conditions.

The results of genetic analyses may be reported in the clinical study report (CSR) or in a separate study summary.

The sponsor will store the DNA samples in a secure storage space with adequate measures to protect confidentiality.

The samples will be retained as described in Section [10.1.11](#).

10.8. Appendix 8: Dosing Guidance for LY3209590 and Insulin Degludec

10.8.1. LY3209590 Algorithm 1 (paper algorithm)

In Study BDCP, a paper dosing Algorithm 1 will be used by investigators for initiating and adjusting LY3209590 to achieve the target FG ≤ 100 mg/dL (< 5.6 mmol/L).

In situations where study participant safety is a concern, investigators may make adjustments to the dose of LY3209590 recommended by the dose-adjustment algorithm in Table 2; however, clinical rationale must be documented in the eCRF and Lilly Medical must be informed about this deviation and associated medical rationale. If the investigator has safety concerns about the algorithm, the investigator is to contact the Lilly CRP.

At the time of site visit, the investigator will assess the study participant's glycemic control for the previous week and, if necessary, inform the study participant about any needed dose adjustment. The dose will be based on the study participant's FG value obtained from the CGM system prior to the morning meal and hypoglycemia documented in the electronic diary in the previous week. Adherence to the dosing algorithm provided for this study is required from Visit 3 (randomization) up to Week 25 and will be monitored periodically by the study team.

General Algorithm Considerations:

- The treat-to-target FG in the algorithm is ≤ 100 mg/dL (< 5.6 mmol/L). LY3209590 dose adjustments will be determined based on the median of the FG (determined from SMBG obtained from the CGM system, referred to as SMBG below) of at least 3 days (up to 7 days) obtained in the previous week leading up to the visit.
- The LY3209590 dose may not be increased if any SMBG reading was documented at ≤ 70 mg/dL (< 3.9 mmol/L) at any time in the preceding week. Dose decreases of 0.5 mg adjustment may be permitted if multiple episodes of hypoglycemia with SMBG ≤ 70 mg/dL (< 3.9 mmol/L) were recorded, or dose decrease of 1 mg if severe hypoglycemia (requiring assistance) occurred, or if any SMBG was documented at ≤ 54 mg/dL (≤ 3.0 mmol/L) in the preceding week.
- In dosing calculations where rounding is required, round to the nearest 0.25 mg.

The starting LY3209590 dose is determined based on both the prior basal insulin dose and baseline fasting glucose. Participants may enter the study using insulin glargine, detemir, or degludec. Consistent with product labeling these insulins may be transitioned on a unit-for-unit basis and for the purposes of this protocol are considered equivalent. Because of the long half-life of LY3209590, the change in fasting glucose response may take several weeks to reach a steady-state response; therefore, to minimize the time needed to achieve the desired target glycemic response, a loading dose strategy will be used for the first dose only. Directions are provided below to convert current basal insulin dose (in Units, U) to the dose of LY3209590 (in mg) for determination of the starting weekly dose and for dose adjustments at subsequent Visits. Examples for Visits 3-6 are provided in *italic text*.

Visit 3 (Randomization Visit):

1. Obtain the prior daily basal insulin dose of insulin glargine, detemir, or degludec assessed during the lead-in period. Calculate the "basal insulin equivalent dose" of LY3209590

(in mg) by dividing the total daily dose of basal insulin (U) by the conversion factor of 7 U/mg.

For example, if a participant uses 35 U of degludec each day, $35 \text{ U} \div 7 \text{ U/mg} = 5 \text{ mg}$ of LY3209590.

2. The dose of LY3209590 mg is then further adjusted according to median baseline fasting glucose and the participant's current basal insulin dose (U) category as shown in Table 1.

For a participant with a median BG value of 155 mg/dL, the dose adjustment for this participant currently using a 35 U dose of degludec would be +1.5 mg.

3. The loading dose is obtained by multiplying the starting total LY3209590 weekly dose (sum of basal insulin equivalent dose and the dose adjustment from Table 1) **CCI**

*In this example, $5 \text{ mg} + 1.5 \text{ mg} = \text{LY3209590 total weekly dose of } 6.5 \text{ mg}$ **CCI** for a total first dose of **CCI**. This first dose, including the loading dose, is used at Visit 3 only.*

Table 1. LY3209590 Dose Adjustment (mg) Using the Median of Baseline Fasting Glucose and Prior Basal Insulin Dose (International Units, U)

Median Baseline Fasting Glucose (mg/dL)	Median Baseline Fasting Glucose ^b (mmol/L)	LY3209590 Dose Adjustment (mg) ^a		
		Basal Insulin Dose $\leq 15 \text{ U}$	Basal Insulin Dose $16 - 30 \text{ U}$	Basal Insulin Dose $> 30 \text{ U}$
<80	<4.4	- 0.25	- 1	- 1.5
80 - 100	4.4 - 5.5	No change	No change	No change
101 - 140	5.6 - 7.7	+ 0.25	+ 0.5	+ 0.75
141 - 180	7.8 - 10.0	+ 0.5	+ 1	+ 1.5
181 - 220	10.1 - 12.2	+ 0.75	+ 1.5	+ 2
>220	>12.2	+ 1	+2	+3

^a This dose adjustment is added to the Basal Insulin Equivalent Dose to obtain the total weekly dose of LY3209590 in mg. The starting total weekly dose of LY3209590 is increased **CCI** to obtain the first loading dose of LY3209590 necessary to reduce the time to achieve target glycemic response.

^b Conversions from mg/dL to mmol/L were rounded off to prevent overlap between threshold ranges and to address that the glucose meter displays 1 significant digit after the decimal when reporting mmol/L readings.

Visit 4 (Week 1)

1. Obtain the starting total weekly dose LY3209590 mg determined at Visit 3. (This is 1/3rd the dose administered at Visit 3.)

From the Visit 3 example, the starting LY3209590 total weekly dose was 6.5 mg.

2. Use Table 2 to determine the dose adjustment needed for Visit 4 after carefully reviewing participant's fasting glucose (3-7 days prior to visit) and hypoglycemia documented since the last LY3209590 dose.

The participant reported no hypoglycemia since the last dose of LY3209590 and had a median FG of 150 mg/dL. Using the Week 1 (Visit 4) column, the LY3209590 weekly dose should be increased by 1 mg.

6.5 mg + 1 mg = 7.5 mg LY3209590 should be administered at Visit 4.

Table 2. Weekly Dose Adjustment of LY3209590 Using the Previous Week's Dose (D) using the Median Fasting Glucose and Hypoglycemic Episodes

Median Fasting glucose (mg/dL) ^a	Median Fasting glucose (mmol/L) ^{a,e}	Week 1 (Visit 4) (2 nd dose)	Week 2 (Visit 5) (3 rd dose)	Subsequent Week ^c
<80 mg/dL or have any nocturnal hypoglycemia or multiple (≥ 3) episodes of hypoglycemia ^d	<4.4 mmol/L or have any nocturnal hypoglycemia or multiple (≥ 3) episodes of hypoglycemia ^d	D ^b – 1.5 mg	D ^b – 1 mg	D ^e – 0.5 mg
80 – 100 mg/dL	4.4 – 5.5	D ^b – 1 mg	D ^b – 0.5 mg	No change
101 – 140 mg/dL	5.6 – 7.7	No change	No change	D ^e + 0.25 mg
141 – 180 mg/dL	7.8 – 10.0	D ^b + 1 mg	D ^b + 0.5 mg	D ^e + 0.25 mg
>180 mg/dL	>10.0	D ^b + 2 mg	D ^b + 1 mg	D ^e + 0.5 mg

^a Based on median fasting glucose from at least 3 fasting glucose readings from previous week.

^b D for Week 1 (Visit 4) is ~~CCI~~ of the dose administered at (Week 0, Visit 3). D for Week 2 (Visit 5) is the dose administered at Week 1 (Visit 4).

^c D for Subsequent Visits is the dose administered one week prior to the current visit.

^d The LY3209590 dose may not be increased if any SMBG reading was documented at ≤ 70 mg/dL (<3.9 mmol/L) at any time in the preceding week. If multiple episodes of hypoglycemia with SMBG ≤ 70 mg/dL (<3.9 mmol/L) were recorded, follow guidance for dose reduction according to the applicable Visit number. Dose decreases of 1 mg should be made when severe hypoglycemia (requiring assistance) occurred, or if any SMBG was documented at ≤ 54 mg/dL (≤ 3.0 mmol/L) in the preceding week.

^e Conversions from mg/dL to mmol/L were rounded off to prevent overlap between threshold ranges and to address that the glucose meter displays 1 significant digit after the decimal when reporting mmol/L readings.

Visit 5 (Week 2)

1. Confirm the dose of LY3209590 mg administered at Visit 4.

From the Visit 4 example, the LY3209590 weekly dose was 7.5 mg.

2. Use Table 2 to determine the dose adjustment needed for Visit 5 after carefully reviewing participant's fasting glucose (3-7 days prior to visit) and hypoglycemia documented since the last LY3209590 dose.

The participant reported no hypoglycemia since the last dose of LY3209590 and had a median FG of 153 mg/dL. Using the Week 2 (Visit 5) column, the LY3209590 weekly dose should be increased by 0.5 mg.

7.5 mg + 0.5 mg = 8.0 mg LY3209590 should be administered at Visit 5.

Visit 6 (Week 3)

1. Confirm the dose of LY3209590 administered at Visit 5 (Week 2).

From the Visit 5 example, the LY3209590 weekly dose was 8.0 mg.

2. Use Table 2 to determine the dose adjustment needed for Visit 6 after carefully reviewing participant's fasting glucose (3-7 days prior to visit) and hypoglycemia documented since the last LY3209590 dose.

The participant reported one episode of nocturnal hypoglycemia since the last dose of LY3209590 and had a median FG of 133 mg/dL. Using the Subsequent Week column in Table 2, and because of the case of nocturnal hypoglycemia, LY3209590 dose should be reduced by 0.5 mg.

8.0 – 0.5 = 7.5 mg of LY3209590 should be administered at Visit 6.

Subsequent visits are managed using the same approach as for Visit 6 (Week 3), always confirming the LY3209590 dose administered at the prior visit, the median fasting glucose during the week prior to the visits, and hypoglycemia status since the last dose of study drug.

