4.3. Justification for Dose

CCI

a single loading dose, followed by weekly dose adjustments is recommended for LY3209590 dosing regimen. The loading dose is determined based on the patient's previously used basal insulin dose, baseline fasting glucose, and available LY3209590 data to inform the **CCI** loading dose strategy. Dose adjustments are based on prior fasting glucose and hypoglycemia events. Alterations to the doses recommended by these dose adjustment algorithms are also under discretion of the investigator and will take hypoglycemia and other study participant safety concerns into account. In case of a deviation from the algorithm-recommended dose, a medical rationale for this deviation must be documented by the principal investigator.

The starting dose for insulin degludec is the same dose as the basal insulin that the study participant used prior to entering the study. The study participant will start a titration phase based on FG and the presence of hypoglycemia or other safety concerns. Dose adjustments will be performed according to a modified Riddle algorithm, which is widely used in clinical trials and clinical practice (Section 10.8).

As it may be desirable to achieve therapeutic goal of LY3209590 in less than 12 weeks with low risk of hyperglycemia, an initiation dose strategy may be appropriate where the first dose sufficient to achieve an efficacious exposure is given initially, followed by individually optimized weekly dose adjustments to achieve target response. Table for Algorithm 1 shows the loading doses, as well as those to be used when adjusting the dose during the dose-individualization visits. See Section 10.8 for description of the dose adjustment algorithms.

Guidance is provided for dosing suggestions for investigators based on FG and hypoglycemia of the study participant (Section 10.8).

Safety of study participants will be closely monitored during the early stages of dose titration to determine whether adjustments to the conversion and dose adjustment algorithm is needed. As additional data emerges, guidance from the sponsor on these dosing algorithms may be modified (Section 10.8).

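### The general bullet in Protocol 10.8.1 permits a flat 0.5 mg LY3209590 cut for multiple hypoglycemia episodes, which disagrees with the governing Table 2 at Weeks 1 and 2

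*Protocol*

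**What the plan says.** Protocol 10.8.1, under General Algorithm Considerations, has one bullet on hypoglycemia. It bars an increase after any reading at or below 70 mg/dL in the preceding week. It then says: "Dose decreases of 0.5 mg adjustment may be permitted if multiple episodes of hypoglycemia with SMBG" at or below that level were recorded, or 1 mg after severe hypoglycemia or any reading at or below 54 mg/dL. The 0.5 mg clause states neither a visit nor a number of episodes.

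Table 2 in the same section sets reductions by visit. Its top row applies if median fasting glucose (FG) is below 80 mg/dL or if participants "have any nocturnal hypoglycemia or multiple" episodes, which the table defines as three or more. The reductions are 1.5 mg at Week 1 (Visit 4), 1 mg at Week 2 (Visit 5) and 0.5 mg in later weeks. The second row, median FG 80 to 100 mg/dL, takes off 1 mg, then 0.5 mg, then nothing.

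Several places make Table 2 the governing text:

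- The opening of 10.8.1 describes investigator adjustments as changes to the dose "recommended by the dose-adjustment algorithm in Table 2".
- Section 4.3 says the Algorithm 1 table shows the loading doses "as well as those to be used when adjusting the dose during the dose-individualization visits".
- Visit 4, step 2 reads "Use Table 2 to determine the dose adjustment needed for Visit 4", and the Visit 5 step has the same form.
- Table 2 footnote d tells sites, when multiple episodes are recorded, to "follow guidance for dose reduction according to the applicable Visit number".

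**The concern.** The bullet's 0.5 mg matches the top row of Table 2 only in the column for later weeks. At Visits 4 and 5 the table asks for a larger cut, and the bullet contains nothing to say that it does not apply there.

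The disagreement errs toward too much insulin, in participants already having hypoglycemia, at the two doses that follow the loading dose. Table 2's cuts are largest at exactly these visits. The product is long-acting: Section 6.7.1 allows up to 10 weeks for washout and Section 8.4 says there is no specific antidote, so an excess weekly dose cannot be taken back the next day.

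There is a smaller consequence for reporting. SAP 5.5 counts prescribed doses that did not follow the algorithm. A 0.5 mg cut at Visit 4 in a top-row participant is allowed by the bullet but departs from Table 2, so its status in that count is unclear.

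**Working it through.** **Inputs, all from Protocol 10.8.1.** Bullet cut *b* = 0.5 mg. Table 2 cut *t*: 1.5, 1 and 0.5 mg in the top row; 1, 0.5 and 0 mg in the FG 80 to 100 row. *D* is the weekly dose to be adjusted. At Visit 4 it is the starting weekly dose: "This is 1/3rd the dose administered at Visit 3". At Visit 5 it is the dose given at Visit 4 (footnote b).

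**The protocol's own example reproduces.** 35 U ÷ 7 U/mg = 5 mg; 5 + 1.5 = 6.5 mg starting weekly dose; 6.5 + 1 = 7.5 mg at Visit 4; 7.5 + 0.5 = 8.0 mg at Visit 5; 8.0 − 0.5 = 7.5 mg at Visit 6, where a nocturnal episode triggers the later-weeks cut.

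**Gap between the two rules.** Dose under the bullet minus dose under Table 2 = (D − b) − (D − t) = t − b. This assumes all readings above 54 mg/dL and no severe event.

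| Situation | Week 1 | Week 2 | Later |
|---|---|---|---|
| Top row met | 1.5 − 0.5 = +1.0 mg | 1.0 − 0.5 = +0.5 mg | 0.5 − 0.5 = 0 |
| Two daytime episodes, median FG 80–100 | 1.0 − 0.5 = +0.5 mg | 0.5 − 0.5 = 0 | 0 − 0.5 = −0.5 mg |
| Two daytime episodes, median FG above 100 | 0 − 0.5 = −0.5 mg | −0.5 mg | −0.5 mg |

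A positive value means that the bullet gives more insulin. The last two lines apply only if *multiple* in the bullet includes two episodes, which it does not say. In the last line Table 2 gives no decrease, because footnote d bars the increase and the top row is not met. There the bullet is the more protective text.

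**On the example doses, top row met.**

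- Visit 4, D = 6.5 mg: bullet 6.0 mg, Table 2 5.0 mg; 1.0 / 5.0 = 20%.
- Visit 5, D = 7.5 mg: bullet 7.0 mg, Table 2 6.5 mg; 0.5 / 6.5 = 7.7%. This isolates the Visit 5 gap. It does not add any excess carried into D from Visit 4.
- Visits 3 and 4 together, with the loading dose 3 × 6.5 = 19.5 mg: 25.5 against 24.5 mg; 1.0 / 24.5 = 4.1%.

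These are milligrams given, not exposure. The elimination figures are blacked out, so no exposure or glucose effect can be derived. The hypoglycemia is also supposed: the protocol's example participant had none at Visits 4 and 5.

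**The case against.** The best reply is that the section already resolves the matter. Footnote d covers multiple episodes and sends the site to the reduction for the visit. The Visit 4 and 5 steps name Table 2, and the bullet is general and only permissive. To go wrong, a site must pass over the visit step, the column heading and the footnote. There are other safeguards: site staff give LY3209590 at the site in Weeks 0 to 8 (Section 4.1.1), bolus doses are corrected before IP is reduced (6.1.2.2), and the study team monitors adherence to the algorithm (10.8.1). All of this stands and limits the scope. It does not make the two texts agree, and a dosing rule should not depend on which paragraph is read.

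A reader might infer three stronger things that the documents do not support.

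- *That sites would overdose participants.* The clause permits a cut and does not prescribe one, a site following the visit steps doses correctly, and no misdosing is documented.
- *That the bullet also causes an excess when a reading is at or below 54 mg/dL or an event is severe.* There the bullet gives 1 mg, and so does footnote d. At Week 1 that 1 mg is less than the top row's 1.5 mg, but this is a tension within Table 2, between the row and its own footnote.
- *That the Week 26 comparison is affected.* Nothing in the documents shows this.

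**Conclusion.** The inconsistency is real, and the sponsor should correct it. At Visits 4 and 5 the bullet permits a smaller cut than Table 2 requires. If the top row is met, with all readings above 54 mg/dL and no severe event, the excess is 1.0 mg at Week 1 and 0.5 mg at Week 2; the two texts agree for that row afterwards. A further 0.5 mg gap at Week 1, with median FG 80 to 100 mg/dL, depends on counting two episodes as multiple.

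The conclusion rests on reading Table 2 as governing, which the text supports in several places, and on reading the bullet as applying at every visit, which follows only from its having no visit limit. The point is a safety-relevant drafting fault of small scope. It does not challenge the algorithm or the primary analysis.

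**What to change.** Replace the 0.5 mg clause in the bullet with:

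*If multiple episodes of hypoglycemia with SMBG ≤70 mg/dL were recorded, reduce the dose per the Table 2 column for the applicable visit; where Table 2 gives no decrease, a 0.5 mg decrease may be permitted.*

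This works whether *multiple* means two episodes or three. It changes no Table 2 dose and keeps the discretionary cut in the cases where the bullet is the more protective text. Leave the bullet's 1 mg clause for severe hypoglycemia or readings at or below 54 mg/dL unchanged.

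Separately, the sponsor should decide whether footnote d's 1 mg or the top row's 1.5 mg applies at Week 1 when both are triggered. If the larger cut is intended, footnote d and the bullet should say so together; changing only the bullet would create a new disagreement.

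The cost is one sentence in the protocol and a notice to sites. Section 4.3 already foresees changes to the dosing guidance, and no SAP change is needed. The notice helps only while participants remain to be dosed at Visits 4 and 5.
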